## Appendix 2. Data Derivation Details

### Appendix 2.1. Definition and Use of Visit Windows in Reporting

Visit label	Protocol defined Window	Visit	Visit window as part of final reporting*
			For efficacy, PD, PK and safety endpoints
Pre-Qualification	NA	0	NA
Screening	NA	1	NA
Run-In	NA	2	NA
Week -2	-14 ± 2	3	
 
Intent is for baseline to be the result closest prior to dosing on randomized regimen on Day 1 [Visit 4]
 
Window for baseline measurements is from Day -20 to Day 1 [Visit 4] pre-dose
 

Week 0 Day 1	1	4	
 
‘Date of assessment’ – ‘Baseline date’ + 1 = [8; 20]; ie, ±6 days
 

Week 2	14 ± 2	5	
 
‘Date of assessment’ – ‘Baseline date’ + 1 = [22 ; 34]; ie, ±6 days
 

Week 4	28 ± 2	6	
 
‘Date of assessment’ – ‘Baseline date’ + 1 = [36 ; 48]; ie, ±6 days with all assessments within 72 hours of last dose
 

Week 6	42 ± 2	7	
 
‘Date of assessment’ – ‘Baseline date’ + 1 = [8 ; 20]; ie, ±6 days
 

1 st Follow-up visit	14 ± 2 days post last dose	8	
 
‘Date of assessment’ – ‘Last Dose date’ + 1 = [24 ; 36]; ie, ±6 days
 

2 nd Follow-up visit	30 ± 2 days post last dose	9	
 
‘Date of assessment’ – ‘Last Dose date’ + 1 = [24 ; 36]; ie, ±6 days
 

Note: \* permitted to be wider than window defined in protocol for purposes of reporting data by nominal visit.

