#### 6.5.6. Rescue Medicine

There is no rescue therapy to reverse the AEs (including identified adverse drug reactions) observed with any of the study interventions; standard medical supportive care must be provided to manage the AEs.

**Participant with T2DM** with *repeated* fasting plasma glucose values >270 mg/dL (15 mmol/L) as reported by the Sponsor-identified central laboratory, at 2 sequential visits (eg, a combination of 2 consecutive scheduled visits *or* 1 scheduled visit followed by an unplanned visit to confirm the elevated result), post randomization, must *either*:

- Have the dose of background metformin for glycemic control optimized, refer to [Section 6.5.1](#) and [Appendix 10.9](#);

- ***Or*** be withdrawn from the study (if ***not*** on metformin prior to randomization) for loss of glycemic control.

***For the identified adverse drug reactions***, guidance to investigators is offered (refer to [Appendix 10.10](#) and [Appendix 10.11](#)) on the basis that reversal of effect towards baseline expected/observed in previous studies with ACCi upon discontinuation of study intervention.

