# **7. DISCONTINUATION OF STUDY INTERVENTION AND PARTICIPANT DISCONTINUATION/WITHDRAWAL**

## **7.1. Discontinuation of Study Intervention**

In rare instances, it may be necessary for a participant to permanently discontinue study intervention (definitive discontinuation). Reasons for definitive discontinuation of study intervention include adverse events or some other (administrative) reason.

If study intervention is definitively discontinued, the participant will not remain in the study for further evaluation. See SoA - [Table 1](#) and SoA - [Table 2](#) for data to be collected at the time of discontinuation of study intervention.

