## **7.2. Participant Discontinuation/Withdrawal from the Study**

A participant may withdraw from the study at any time at his/her own request. Reasons for discontinuation from the study include the following:

- Refused further follow-up;
- Lost to follow-up;
- Death;

- Study terminated by Sponsor;
- Discretion of the Investigator or Sponsor for safety or behavioral reasons, or the inability of the participant to comply with the protocol-required schedule of study visits or procedures at a given study site.

As soon as practically possible *after* the decision to withdraw from the study, an on-site visit should be considered:

- Participants should be questioned regarding their reason for withdrawal;
- See SoA – [Table 1](#) and SoA - [Table 2](#) – for assessments to be collected at the time of study discontinuation and follow-up for any further evaluations that need to be completed.

In this study, any participant who discontinues participation *after the PreQ visit but prior to randomization and administration of the 1st dose of double-blind, double-dummy study intervention* will have no additional procedures completed.

The early discontinuation visit applies only to participants who are randomized and then are prematurely withdrawn from the study. Participants should be questioned regarding their reason for withdrawal.

The participant will be permanently discontinued both from the study intervention and from the study at that time.

If a participant withdraws from the study, he/she may request destruction of any remaining samples taken and not tested, and the investigator must document any such requests in the site study records and notify the Sponsor accordingly.

If the participant withdraws from the study and also withdraws consent (see [Section 7.2.1](#)) for disclosure of future information, no further evaluations should be performed and no additional data should be collected. The Sponsor may retain and continue to use any data collected before such withdrawal of consent.

Lack of completion of all or any of the withdrawal/early termination procedures will not be viewed as protocol deviations so long as the participant's safety was preserved.

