### 7.2.1. Withdrawal of Consent

Participants who request to discontinue receipt of study intervention will remain in the study and must continue to be followed for protocol-specified follow-up procedures. The only exception to this is when a participant specifically withdraws consent for any further contact with him or her or persons previously authorized by the participant to provide this information. Participants should notify the investigator in writing of the decision to withdraw consent from future follow-up, whenever possible. The withdrawal of consent should be explained in detail in the medical records by the investigator, as to whether the withdrawal is only from further receipt of study intervention or also from study procedures and/or posttreatment study follow-up, and entered on the appropriate CRF page. In the event that vital status (whether the participant is alive or dead) is being measured, publicly available information should be used to determine vital status only as appropriately directed in accordance with local law.

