#### Intercurrent Events:

- Non evaluable baseline – All data collected post-randomization will be excluded.
- Withdrawal from study intervention after randomization – All data collected after a participant stops taking study intervention will be included.
- Prohibited medications – All assessments after a participant receives prohibited medications that would modulate the endpoint will be omitted from the analysis. The list of concomitant medications would be reviewed prior to database lock to determine which would be classed as “prohibited” for this estimand.

- Inadequate compliance – All randomized/evaluable participants, *regardless of the level of compliance*, will have their endpoint measurement used as recorded in the analysis.

Population level summary:

- The population level summary will be the mean difference in natural log-transformed relative change from baseline between DGAT2i + ACCi groups and placebo groups for the endpoint of interest *over time*.

### 2.1.3. Estimand 3

For a given endpoint, the estimand will be the estimated population based average treatment effect on ***change from baseline*** for DGAT2i + ACCi relative to placebo ***over time*** for all randomized/evaluable participants.

Intercurrent Events:

- Same as Estimand 2.

[figure not shown]
Population level summary:

- Same as Estimand 2 but with the mean difference in change from baseline between DGAT2i + ACCi groups and placebo groups for the endpoint of interest *over time*.

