#### Special consideration:

- For participants withdrawn early, the follow-up visit window (F/U) should be excluded from windowing algorithm, and the visit label is defined in accordance with the nominal label as recorded on the “E\_TERM/FOLLOW\_UP” Administration CRF.
- If 2 or more observations fall within the visit window for Week N, the observation used will be the one closest to Day 7N (randomization day is Day 1). If the 2 closest observations are equidistant from Day 7N, the earlier observation will be used.

An assessment is considered ‘on treatment’ if the following is true:

- ‘Date (time when databased) of assessment’ > ‘Baseline date (time)’ and ≤‘Last dose date (time)’

All PD endpoints defined in section 6.1, 6.2.1, 6.3.1-6.3.9, 6.6.4.1, 6.6.4.2 are applied for visit window. For safety data (including laboratory analytes), there are no summary outputs planned by visit window; and for Vitals/12-lead ECG data as well as PK data, summaries will be generated based on reported nominal visit (and *not* use above visit windowing).

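### The SAP's Week 6 window drops off-drug values that Estimands 2 and 3 include, and Protocol 7.1 and 7.2 contradict 7.2.1 for participants who ask to stop

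*SAP*

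**What the plan says.** **Estimands.** Estimand 2 covers fasting triglycerides, the secondary endpoint. On withdrawal from study intervention, Protocol 9.1.1 and SAP 2.1.2 both state: "All data collected after a participant stops taking study intervention will be included". A further bullet keeps values as recorded whatever the level of compliance. Estimand 3 (HbA1C, FPG, FPI, HOMA-IR; SAP 2.1.3) takes its intercurrent-event rules from Estimand 2. Only Estimand 1, which covers imaging, excludes data after drug is stopped.

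**Windows.** In SAP Appendix 2.1 the Day 36-48 window carries the extra condition "with all assessments within 72 hours of last dose". The scope sentence reads: "All PD endpoints defined in section 6.1, 6.2.1, 6.3.1-6.3.9, 6.6.4.1, 6.6.4.2 are applied for visit window". Section 6.2.1 is triglycerides and the 6.3 range includes the other Estimand 2 and 3 endpoints. No exception is made by estimand. On early withdrawal the appendix says: "For participants withdrawn early, the follow-up visit window (F/U) should be excluded from windowing algorithm", and it takes the visit label from the termination/follow-up CRF.

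**Retention.** Protocol 7.1: "If study intervention is definitively discontinued, the participant will not remain in the study for further evaluation". Protocol 7.2: "The participant will be permanently discontinued both from the study intervention and from the study at that time". Protocol 7.2.1: "Participants who request to discontinue receipt of study intervention will remain in the study and must continue to be followed for protocol-specified follow-up procedures".

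**The concern.** A visit window should place a date on a visit. A last-dose condition does something else: it filters on treatment status, which is what the withdrawal bullet of Estimands 2 and 3 already governs, and that bullet says to include. A programmer holding an off-drug Week 6 triglyceride value cannot obey both.

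The Week 6 triglyceride comparison bears on the study's aim, the lowest DGAT2i dose that mitigates the ACCi-induced rise, and on the decision about Part 2. As written, the result could be labelled as including off-drug data while leaving some of it out.

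The retention passages add a second problem. Whether an off-drug Week 6 sample exists at all for someone who asks to stop depends on which section the site follows.

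**Working it through.** **1. Which row carries the condition.** The table's rows are displaced in the text as read, but the day ranges settle it: 14 ± 6 = 8-20, 28 ± 6 = 22-34, 42 ± 6 = 36-48. Only 36-48, centred on Day 42, carries the 72-hour limit, so it belongs to Week 6. The displacement is not counted as an error in the plan.

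**2. Day arithmetic.** Take 72 hours as 3 days. With last dose on Day L, a Week 6 value on Day a survives if 36 ≤ a ≤ 48 and a − L ≤ 3.

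- L before Day 33: no usable Week 6 value.
- L before Day 37: none within the protocol visit range 42 ± 2 (Day 40-44).
- L before Day 39: a Day 42 value is lost.

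Example: last dose Day 20, samples on Days 28 and 42. The Day 28 value (8 days off drug) falls in 22-34 and is used as Week 4. The Day 42 value (22 days off drug) is included by Estimand 2 and excluded by the window.

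**3. Who is affected.** The participant must be more than 72 hours off drug and still sampled at Week 6. Two routes fit the text: a requested stop retained under 7.2.1, and a participant who stops taking tablets but keeps attending, whose values the compliance bullet says to use.

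**4. Early-termination samples.** The special rule removes the follow-up window and relies on a CRF label. It does not say whether the 72-hour condition still applies. Nor does it say which triglyceride model visit (Weeks 2, 4, 6 or Follow-Up; Protocol 9.4.2) the sample becomes.

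**5. The plan's own power figure.** Inputs from Protocol 9.2.1: 15 per group, log SD 0.221, 25% decrease, one-sided 5%. δ = |ln 0.75| = 0.2877; SE = 0.221 × √(2/15) = 0.0807; δ/SE = 3.565; power = Φ(3.565 − 1.645) = 97.3% (96.7% by noncentral t, 28 df). The stated >90% reproduces. It concerns liver fat under Estimand 1 and does not depend on this point.

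**6. Illustrative size.** The documents give no triglyceride SD or stopping rate. Assume that a fraction p of the active group stops, independently of triglyceride level, with full reversal by Week 6 (Protocol 2.2.1 reports reversal in 1 to 2 weeks for ACCi alone). With on-drug placebo-adjusted change e, the estimate with off-drug values in is 100 × {exp[(1 − p) ln(1 + e)] − 1}.

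| On-drug change e | p = 1/18 | p = 2/18 | p = 3/18 |
|---|---|---|---|
| +10% | +9.4% | +8.8% | +8.3% |
| +28% | +26.3% | +24.5% | +22.8% |
| +50% | +46.7% | +43.4% | +40.2% |

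The +28% is the upper 90% limit cited in Protocol 4.3.1 for a different dose, and 3/18 is the plan's allowance for non-evaluable participants. Both are used for illustration only. With off-drug Week 6 values dropped, the estimate stays near e, so at +28% the gap is 28 − 26.3 = 1.7 to 28 − 22.8 = 5.2 points. Off-drug Week 4 values remain in the MMRM and would pull the Week 6 estimate part of the way back, so these gaps lean high.

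**7. Against precision.** Assume residual log SDs of 0.46 (active) and 0.32 (placebo) with 15 per arm. SE = √[(0.46² + 0.32²)/15] = 0.145, and the 80% half-width is 1.294 (t, 70 df) × 0.145 ≈ 0.187. Around an assumed +40.5%: 1.405 × exp(±0.187) = 1.165 and 1.694, about +16% to +69%. The same half-width around +28% gives about +6% to +54%.

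**The case against.** - **The conflict is narrow.** This stands. Under 7.1 and 7.2 a definitive stopper leaves the study, so no later Week 6 sample is taken. Including all data collected is then obeyed trivially. The firm clash needs someone off drug and still sampled at Week 6.
- **The early-withdrawal rule may already handle it.** A withdrawn participant's last sample can be read as CRF-labelled rather than windowed. That is one reading of an ambiguous sentence. It does not cover participants who are still attending, and it leaves the model visit open.
- **The SAP may modify the protocol.** Protocol Section 9 allows this. But the SAP repeats the inclusion bullet itself, so the contradiction lies inside the SAP.
- **7.1 and 7.2.1 may address different cases.** 7.1 gives adverse events and administrative reasons as the reasons for stopping; 7.2.1 concerns requests, and its follow-up procedures may not mean the Week 4 and 6 draws. This narrows the conflict to requested stops. It does not remove it, because the sentence in 7.1 is unconditional and 7.2 also covers withdrawal at the participant's own request.
- **Other sources may bear on it.** The SAP's version history cites two PACLs (01-Jul-2020 and 22-Jan-2021) that are not available here, and Protocol Appendix 10.10 on triglyceride management is not readable here.

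A reader might go further and infer that participants stopped at the triglyceride threshold (Protocol 8.2.8.1) or withdrawn for fasting glucose (6.5.6) are caught in the contradiction, with sizeable bias. The readable text does not support that. Those stops are not participant requests, so 7.1 or 7.2 applies. Their absent Week 6 values are ordinary missing data under the MMRM, not values discarded by the window.

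**Conclusion.** The point holds in limited form, at minor to moderate severity. For an off-drug participant still sampled at Week 6, Estimands 2 and 3 and SAP Appendix 2.1 give incompatible instructions, and Weeks 2 and 4 are treated differently from Week 6 without a stated reason. For requested stops, Protocol 7.1 and 7.2 cannot be followed together with 7.2.1. This review takes no position on which is right.

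The case rests on the conflicting instructions rather than on the size of the bias. At +28% on drug the gap is about 2 to 5 points, assuming full reversal, 1 to 3 of 18 stopping and stops unrelated to triglycerides. The group in which the texts clash may well be smaller than that.

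A reader might also infer that the window flatters an inadequate dose. For a net on-drug rise the reverse is true: dropping reversed values makes the rise look larger, which works against declaring mitigation. No formal tests are planned (Protocol 9.1.2), and the primary endpoint and its power are unaffected.

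**What to change.** **Wrong as written; choose one.**

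- (a) In SAP Appendix 2.1, confine the 72-hour condition to Estimand 1 endpoints.
- (b) If the condition is meant for all endpoints, restate the withdrawal bullet of Estimand 2 (Protocol 9.1.1, SAP 2.1.2) and Estimand 3 (SAP 2.1.3) to match. Apply a last-dose condition at Weeks 2 and 4 as well, and say how Follow-Up, which is off drug by design, enters the model.

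**Under either option**, state which model visit an early-termination sample is assigned to, and report the number who stopped drug by arm beside the triglyceride estimates.

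**Separately**, reconcile Protocol 7.1, 7.2 and 7.2.1 with each other and with Estimands 2 and 3, checking the PACLs and Appendix 10.10 first. No stopping or withdrawal threshold needs to change for this.

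**Cost.** Option (a) is one table entry and one sentence in the SAP. Option (b) also edits estimand text in both documents. Neither changes the sample size or adds visits. Reconciling the retention passages may cost more. If the outcome is that participants who stop are followed for further scheduled draws, that changes study conduct, and Protocol 10.1.1 requires IRB/EC approval of amendments.

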#### Special consideration:

- For participants withdrawn early, the follow-up visit window (F/U) should be excluded from windowing algorithm, and the visit label is defined in accordance with the nominal label as recorded on the “E\_TERM/FOLLOW\_UP” Administration CRF.
- If 2 or more observations fall within the visit window for Week N, the observation used will be the one closest to Day 7N (randomization day is Day 1). If the 2 closest observations are equidistant from Day 7N, the earlier observation will be used.

An assessment is considered ‘on treatment’ if the following is true:

- ‘Date (time when databased) of assessment’ > ‘Baseline date (time)’ and ≤‘Last dose date (time)’

All PD endpoints defined in section 6.1, 6.2.1, 6.3.1-6.3.9, 6.6.4.1, 6.6.4.2 are applied for visit window. For safety data (including laboratory analytes), there are no summary outputs planned by visit window; and for Vitals/12-lead ECG data as well as PK data, summaries will be generated based on reported nominal visit (and *not* use above visit windowing).

## Appendix 2.2. Endpoint Derivations

### Appendix 2.2.1. % Liver Fat using MRI-PDFF

For each participant in the study, the Whole Liver PDFF (WLPDFF in %) will be calculated from the pre-defined individual segmental PDFF (SPDFF in %) measured in Segments I, II, III, IVa, IVb, V, VI, VII and VIII as follows:

$$\text{WLPDFF} = (\text{SPDFF Segment I} + \text{SPDFF Segment II} + \text{SPDFF Segment III} + \text{SPDFF Segment IVa} + \text{SPDFF Segment IVb} + \text{SPDFF Segment V} + \text{SPDFF Segment VI} + \text{SPDFF Segment VII} + \text{SPDFF Segment VIII}) / (\text{number of segments assessed and no missing/mapping at Baseline, and on Week 6})$$

[figure not shown]
**Note:** If any negative values is reported by the central vendor for an individual segment, the value of this segment will be imputed to “0” before inclusion into derivation of whole liver PDFF. However, the negative value, as offered by the central vendor, will be included in the listing.

#### **Calculation Rule for % Liver Fat when Assessed with MRI-PDFF:**

[figure not shown]
WLPDFF will be calculated on mapping no missing segments at Baseline, and on Week 6.

For instance,

if results are reported for all segments at Baseline, and on Week 6 (see below),  
The number of segments assessed is equal to 9.

If at Baseline, all segment data are available, but, on Week 6 only 7 segments have results reported, WLPDFF will be calculated at Baseline, and on Week 6 and using the matching individual segments providing values on **both** weeks. For instance, based on the schema below, Segment II and Segment V will not be used to calculate WLPDFF on any of the time points reported. In this case, WLPDFF will be calculated using data in the 7 segments reported at **both imaging** visits.

WLPDFF and individual % liver fat measured in each individual segment will be listed. WLPDFF will be summarized by actual treatment, and Week as described in [Section 5.2.2](#).

### Appendix 2.2.2. Compliance

Compliance with double-blinded study medication will be calculated using data entry exclusively from the **Double Blinded treatment** CRF pages on Week 2, Week 4 and Week 6.

Compliance between any two visits in the study will be calculated as:

$$\% \text{ Compliance} = \frac{100 \times (\text{# of pills actually taken since the previous visit})}{(\text{# of pills expected to be taken since the previous visit})}$$

The **# of pills actually taken since the previous visit** will be taken directly from the “Actual Dose” field in the Double Blinded treatment CRFs (sites will be instructed to enter the total number of tablets that the participant has consumed since the last on-site visit).

The **# of pills expected to be taken since the previous visit** = (Date of current visit – Date of previous visit)\* (Expected Tablets per day in each part)

Compliance across the overall study treatment period will be calculated as:

$$\% \text{ Compliance} = \frac{100 \times (\text{# of pills actually taken during the double-blind treatment phase})}{(\text{# of pills expected to be taken during the double-blind treatment phase})}$$

The **# of pills actually taken during the double-blind treatment phase** = sum of all “Actual dose” fields for all visits during the double-blind treatment phase (ie, the sum of the total number of tablets that the participant has consumed during the double-blind treatment phase).

The **# of pills expected to be taken during the double-blind treatment phase** = (Week 6 (V7) or Early Term visit date – Baseline visit date (V4))\* (Expected Tablets per day in each part)

 To be determined for part 2. For instance in Part 1 the total daily dose will be administered using 6 tablets

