**Table 1. Procedures for Part 1 and *Optional* Part 2**

Visit Identifier	PreQ	SCR	Run-In	Baseline	Treatment Phase [All, except Imaging procedures, before morning dose of blinded study intervention]					Follow-up		Study D/C
					-4	-2	0 Day 1	2	4	6	8	
Weeks a Relative to Dosing on Day 1	0	1	2	3	4	5	6	7	8	9		
Informed consent & demography	x	x										
(Update) Medical & Medication Information	x	x	x	x	x	x	x	x	x		x	
Liver fat and stiffness (via FibroScan ® ) c,d	x	x		x				x				
Liver fat via MRI-PDFF c,d				x				x				
Liver fat and stiffness (via Acuson Sequoia ® ) c,d				x				x				
Physical Exam (PE) e	x	x		x	x	x	x	x	x	x		x
Assess alcohol intake (AUDIT questionnaire)	x	x			x			x				
Assess correct use of contraception, where applicable			x	x	x	x	x	x	x	x		x f
Counseling on diet/exercise guidelines			x		x							
Open-ended inquiry for adverse events (AEs)	x	x	x	x	x	x	x	x	x	x	x	
Single supine 12-lead ECG	x	x			x			x	x	x		x
Single seated vitals (BP & pulse rate) and body weight	x	x			x			x	x	x		x
Registration of visit in study (via IRT)	x	x	x	x	x	x	x	x	x	x	x	x
Onsite administration of study intervention, with meal g				x	x	x	x	x				
Dispensation (via IRT) of study intervention				x	x	x	x					
Compliance check of returned study intervention h					x g	x	x	x				x

- a. Defined **relative to Day 1** with permitted  $\pm 2$ -day window for each visit starting at Baseline/Visit 3; for example: Week -2 = 14 ( $\pm 2$ ) days before Day 1; Week 4 = 28 ( $\pm 2$ ) days post Day 1.
- b. Telephone contact can be switched to on-site visits for follow-up of AEs and/or abnormal laboratory tests; Week 10 visit at  $\geq 28$ - and  $\leq 32$  days post last dose (Day 30 $\pm 2$  days).
- c. Procedure performed following  $\geq 4$ -hour fast (except water), as part of on-site visit *or* separate visit(s) to Imaging/Radiology facility; attempts to be made to perform Week 6 assessment within  $\pm 2$ -hour window of time of 1st assessment (PreQ for FibroScan® and Baseline/Visit 3 for MRI-PDFF and Acuson Sequoia®).
- d. Baseline assessments performed at or after Visit 3 and before dosing on Day 1/Visit 4; Week 6 performed  $\leq 2$  days post last dose of blinded study intervention.

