### 6.5.2. Standard Analyses

- Listings that account for all participants who offered at least consent for pre-qualification and whether screen failed (at any point *after* the consent offered at the prequalification visit and *before* randomization on Day 1/Week 0/Visit 4 will be presented).
- Study Conduct and Participant Disposition: The number of participants randomized, treated, completing and discontinuing from the study. For participants who did not complete the study, the reasons for withdrawal from the study will be presented.
- Baseline Characteristics: Demographic characteristics such as participant age, gender, height, weight, body mass index (BMI), race, and total per arm, by treatment group will be tabulated. ***In addition,***
  - The number of participants randomized and treated will be summarized per arm, by treatment group, with each of the pre-defined medical history terms (ie, T2DM, Hyperglycemia, HDL increased, TG increased, hypertension, waist circumference increased).
  - The number of participants in each analysis population will be included in each summarized output (for safety set, PK concentration set, and for each estimand strategy) by actual treatment.
- Overall compliance (Day 1 to Week 6 or premature termination during treatment phase) will be summarized by frequency (%) in the following two categories by treatment. Formula to compute compliance is defined in Appendix 2.4.
  - < 80%
  - ≥ 80% (and up to 110%)

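### The SAP's overall compliance formula contradicts itself on which tablet counts enter the numerator, and for early terminators it counts days after dosing ended as missed doses

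*SAP*

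**What the plan says.** SAP Appendix 2.2.2 opens with a source rule: compliance "will be calculated using data entry exclusively from the" Double Blinded treatment "CRF pages on Week 2, Week 4 and Week 6". No Early Term page is named.

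For the whole treatment period, the same appendix defines the numerator as the sum of the Actual Dose fields over all double-blind visits, and explains this as "the sum of the total number of tablets that the participant has consumed during the double-blind treatment phase". Expected tablets are the days from Visit 4 to Week 6 "or Early Term visit date", multiplied by tablets per day. The footnote fixes the multiplier: "For instance in Part 1 the total daily dose will be administered using 6 tablets".

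SAP 6.5.2 applies this to people who stop early: "Overall compliance (Day 1 to Week 6 or premature termination during treatment phase) will be summarized by frequency". It gives two categories by treatment, below 80% and at least 80% up to 110%, and refers to Appendix 2.4 for the formula, which is in Appendix 2.2.2.

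In the protocol, the Table 1 row "Compliance check of returned study intervention" is marked at Study D/C as well as at the treatment visits. Protocol 6.4 defines the post-randomization compliance period as Day 1 to the last day of dosing or Week 6.

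**The concern.** For a Week 6 completer the three pages and the visit dates cover the same period. For an early terminator they need not. If the source rule governs, tablets taken between the last Week 2 or Week 4 page and the Early Term visit are left out of the numerator, while their days stay in the denominator. If the all-visits definition governs, those tablets are counted. Two programmers could report very different figures for the same participant.

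A second problem does not depend on that choice. The denominator ends at the Early Term visit, so any days between the last dose and the visit are scored as missed doses, even where the participant had been told to stop.

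At stake is the compliance table by arm, which readers use to judge whether each regimen was taken. Triglyceride rise and platelet fall are identified ACCi reactions with stopping rules (Protocol 2.3.1 and 8.2.8), so a distortion could fall unevenly across arms.

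**Working it through.** The documents state no compliance result, so there is no figure to reproduce. The formula is applied to a hypothetical participant.

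**Inputs.** 6 tablets per day (SAP Appendix 2.2.2). Week 2 and Week 4 visits at 14 and 28 days after Day 1, each ±2 days (Protocol Table 1). Cut-off 80% (SAP 6.5.2). Assumptions: every tablet is taken, dosing continues up to the Early Term visit at day *t* after Day 1, and visits are on nominal days.

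**1. Numerator.** Expected tablets = 6*t*. On the literal reading the tablets counted are 0 for *t* < 14 (if an absent page is scored as zero), 14 × 6 = 84 for 14 ≤ *t* < 28, and 28 × 6 = 168 for 28 ≤ *t* < 42.

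| *t* | Counted (literal) | Expected | Literal | With Early Term count |
|---|---|---|---|---|
| 10 | 0 | 60 | 0% | 100% |
| 17 | 84 | 102 | 82.4% | 100% |
| 18 | 84 | 108 | 77.8% | 100% |
| 24 | 84 | 144 | 58.3% | 100% |
| 27 | 84 | 162 | 51.9% | 100% |
| 28 | 168 | 168 | 100% | 100% |
| 35 | 168 | 210 | 80.0% | 100% |
| 36 | 168 | 216 | 77.8% | 100% |
| 41 | 168 | 246 | 68.3% | 100% |

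The 80% line is crossed after 14/0.8 = 17.5 days and after 28/0.8 = 35 days. The literal score is below 80% on days 18-27 (10 days) and 36-41 (6 days), and on days 1-13 if an absent page counts as zero: 13 + 10 + 6 = 29 of 41 days. It is at least 80% on days 14-17 and 28-35, which is 12 days. If days 1-13 are treated as missing, 16 of the remaining 28 days are below 80%. Moving the two visits within their ±2-day windows changes 29 to between 28 and 30.

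**2. Denominator end date.** Now include the Early Term count. With *L* full days of dosing and the visit *g* days later, compliance = *L*/(*L* + *g*). It falls below 80% when *g* exceeds *L*/4.

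- *L* = 10, *g* = 5: 60/90 = 66.7%.
- *L* = 20, *g* = 5: 120/150 = 80.0%.
- *L* = 20, *g* = 10: 120/180 = 66.7%.
- *L* = 30, *g* = 8: 180/228 = 78.9%.

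**3. Categories.** Over 42 days the expected count is 42 × 6 = 252, and 110% of that is 277.2. A count of 278 (26 extra tablets) belongs to neither category. One spare 7-day card, 7 × 6 = 42 tablets, goes out at each dispensation (Protocol 6.1), so enough tablets are in hand.

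**4. Check on the repair.** Replacing the visit date by the last-dose date with no further change would over-score. Someone who takes both doses on a last day 5 days after Visit 4 has taken 6 × 6 = 36 tablets against 5 × 6 = 30 expected, or 120%. Adding one day gives 36/36 = 100%. If only the morning dose (3 tablets) was taken that day, 33 were taken, and expected tablets must be cut by 3 as well.

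**The case against.** The strongest defence is that the overall numerator has its own, more specific definition: all visits, all tablets consumed. On that reading a participant who doses up to the Early Term visit scores 100% on any day, and the opening sentence is only loosely worded. The CRF is also not available to the reader; if the Study D/C count is entered on one of the named pages, even the literal rule includes it. Both points stand. They reduce the numerator problem to a contradiction that needs settling. They do not remove it, because the word exclusively is there.

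On the denominator, Protocol 7.2 asks that an on-site visit be considered as soon as practically possible after the decision to withdraw, and no document gives a figure for the delay. That limits the likely size. It does not explain why the SAP's end point differs from Protocol 6.4.

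A reader might infer that all fully adherent early terminators would be shown as non-compliant. Even the literal reading does not give that: days 14-17 and 28-35 score at least 80%, and the result for days 1-13 depends on scoring an absent page as zero, which the SAP does not say to do.

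A reader might also infer a false adherence gap of up to 3/18 = 17 percentage points against an active arm, from the allowance of 18 randomized for 15 evaluable. That allowance covers loss of evaluable data for any reason. The figure would need all three losses in one arm to be fully adherent early terminators leaving on unfavourable days. Protocol 7.1 calls definitive discontinuation rare, loss of glycemic control can lead to withdrawal in any arm (Protocol 6.5.6), and 29 of 41 is a count of days and not a probability.

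**Conclusion.** The point holds as an internal contradiction together with two smaller defects that survive either reading.

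- The numerator source is contradictory. A fully adherent participant leaving on day 24 is reported as 58% or 100%, depending on which sentence the programmer follows.
- The denominator end date departs from Protocol 6.4. The shortfall depends on the delay between last dose and visit, which is unknown; 20 days of dosing with a 10-day delay gives 67%.
- Compliance above 110% has no category.

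Each misclassified participant moves an arm's below-80% figure by 1/18 = 5.6 percentage points. These results assume full adherence and nominal visit days; the first also assumes dosing up to the Early Term visit.

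A reader might infer that the primary analysis is at risk, because Estimand 1 uses the same 80% limit. The documents do not support that. MRI-PDFF is scheduled at Baseline and Week 6 and not at Study D/C, and Estimand 1 already excludes data after study intervention stops. Estimand 2, and Estimand 3 which follows it, use data whatever the compliance. The effect is on the descriptive table in SAP 6.5.2, with little or none on the primary result.

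**What to change.** In SAP Appendix 2.2.2:

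- Name the Study D/C (Early Term) tablet count as a numerator source beside the Week 2, 4 and 6 pages, so that the source rule agrees with the all-visits definition. State how a missing count is handled.
- For early terminators, set expected tablets to (last double-blind dose date − Visit 4 date + 1) × tablets per day, reduced if only the morning dose was taken on the last day. Keep the visit-date rule for Week 6 completers.

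In SAP 6.5.2, add a category above 110% and correct the cross-reference from Appendix 2.4 to Appendix 2.2.2.

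The cost is SAP wording and a small program change. The tablet count is already scheduled at Study D/C. The last-dose date is already needed for the follow-up windows in SAP Appendix 2.1; whether only the morning dose was taken on that day has to be recoverable from the dosing records. The added day must not be left out, since without it early stoppers would be over-scored.
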